2. Determine whether prehospital tranexamic acid as compared to placebo results in a lower incidence of 24 hour mortality, acute lung injury, multiple organ failure, nosocomial infection, shock parameters, early resuscitation and transfusion needs, early seizures and pulmonary embolism.
3. To explore potential novel mechanisms by which tranexamic acid alters the inflammatory response to injury independent of effects on hyperfibrinolysis including effects on platelet and leukocyte activation via flow cytometry, measurements of plasmin levels and subsequent plasmin mediated complement activation and the early inflammatory cytokine response to trauma.
4. Determine whether different dosing regimens of tranexamic acid upon arrival in the hospital are associated with improvements in hyperfibrinolysis, markers of coagulopathy, clinical outcomes, and the early inflammatory response.

Pre Trial Start Period: The PIs and Site investigators will obtain FDA approval followed by approval for exception from consent for emergency research from their respective IRBs. The University of Pittsburgh as coordinating center will create a web based data entry platform for the trial.

Year 1: Following a 1 month training period for participating centers on enrollment procedures and TEG analysis, trial enrollment will begin with an estimated 330 patients enrolled by years end. Blood samples will be batched for plate assay analysis at the University of Pittsburgh and prospective outcomes data will be obtained,

entered and integrity verified. First interim analysis will occur at 1/3 of total patient enrollment. Those exploratory aim measurements that require fresh blood samples will occur at the University of Pittsburgh alone.

Year 2: An estimated additional 330 patients will be enrolled (total=660) by end of the second year and blood samples will again be batch analyzed for plate assay analysis. Continued prospective data collection and integrity verification for clinical outcomes will occur. A second interim analysis will occur after 2/3 of total patient enrollment. Exploratory aim measurements which require fresh blood samples will occur at the University of Pittsburgh alone.

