levels, markers of complement activation, HMGB1 levels and the early inflammatory cytokine response as compared to standard dosing or abbreviated dosing.

F. Project Milestones:

The proposal is for a 3 year trial. The FDA approval process will be initiated after notification of proposal funding. Community notification and other procedures associated with exception from consent for emergency research will be initiated and completed prior to IRB approval at all institutions. Following final IRB approval a 1.5 month startup period will be utilized to verify and educate all centers prior to beginning enrollment. A data entry web based platform will be created during this same time period. Enrollment will occur for 33 months (2.75 years) with prospective data entry of laboratory and TEG measurements, clinical outcomes, transfusion requirements and demographic and injury characteristics. Serum for cytokine and ELISA measurements will be batched and sent to the University of Pittsburgh on an annual basis. We expect approximately 70 patients per year per institution on average. Flow cytometry for platelet and leukocyte activation and RT-PCR may be performed at the University of Pittsburgh prospectively on a subset of patient samples. Enrollment will be monitored on a semi-annual basis for each participating center. Data safety and monitoring over the course of the clinical trial will fall under the responsibility of an independent data safety and monitoring board (DSMB). Interim analysis will occur at 33% and 66% of patient enrollment. A 1.5 month data cleaning and wind down will occur once enrollment has been completed, allowing data analysis and manuscript preparation.

G. Military Significance/Public Purpose:

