H.5.1. *Prehospital Phase Randomization:* Individual patients meeting criteria while en route via emergency medical transport will be randomized using an allocation sequence block size of 8 to either 1 gram of tranexamic acid or placebo diluted in 100cc of normal saline given over approximately 10 minutes. A single prehospital treatment box containing ascending numerically labeled (1-8) treatment packs (randomized with a computer random number generator) will be distributed to each respective helicopter base (or station in the case of ground ambulance). In an ascending numerical order fashion treatment packs will be utilized for enrolled patients. The box and treatment pack # will be recorded by research staff upon arrival for all randomized patients. The patient and all treatment and research staff will be blinded to the treatment arm. All intervention vials will be covered to obscure view of vial contents to prehospital staff giving the intervention and amber colored syringes will be utilized to maintain blinding. IDS at the University of Pittsburgh will be unblinded to the prehospital intervention. Additionally, the pharmacy at each respective participating center will have access to the prehospital randomization/assignment scheme once the prehospital intervention box and treatment # are provided to them by the accepting research staff at each participating center.

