H.5.2. *In-hospital Phase Allocation:* Using a web based, randomization assignment program built specifically for the trial, research staff will provide and input the prehospital intervention box # and treatment pack # into the web based platform at each site and be provided the In-hospital treatment allocation to be utilized for the second phase intervention. IDS at the University of Pittsburgh and each respective pharmacy at the participating sites will be provided with the random allocation sequence and will be unblinded to the in-hospital allocation assignment. The accepting research staff and pharmacy will verify they have the same in-hospital phase treatment assignment as an additional check to the allocation assignment. An allocation sequence based upon a block size of 9 again generated with a computer random number generator will be utilized for those who received prehospital Tranexamic Acid. Each respective IDS or pharmacy will prepare the in-hospital phase treatment (approximate 10 minute and 8 hour infusion). The patient and all treatment and research staff will be blinded to the treatment that is received.

H.6. Blinding: The trial is a double blinded trial for both the prehospital phase and in-hospital phase interventions. The participants, investigators, research coordinators and staff, and persons having any contact with the patients will be blinded to study treatment assignments. The IDS at the University of Pittsburgh will be unblinded to the prehospital phase treatment arm and the respective pharmacy at each center will be unblinded once the treatment prehospital treatment information is provided to them by research staff. Both IDS at the University of Pittsburgh and the respective IDS or pharmacy at each center will be unblinded to the in hospital treatment assignment.

H.7. Prehospital Standard Operating Procedures: To minimize over exuberant crystalloid resuscitation during the prehospital phase of treatment after enrollment, further crystalloid resuscitation post-intervention will follow a 'goal directed' standard operating procedure (SOP). Crystalloid infusion following the intervention will be based upon hemodynamic status (SBP < 90mmHg) with infusion of 500cc boluses of crystalloid for those patients with persistent hypotension. Normotensive patients will receive crystalloid infusion at maintenance rate. (Figure 13. above) All crystalloid volumes will be monitored relative to transport time for all

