I.5. Laboratory/Mechanistic Outcome Methods/Definitions: All measurements will be performed within 6 hours of arrival and at 12 and 24 hours post injury (+/- 12 hours) for the randomized dosage regimen comparison. One more additional blood sample will be collected at 72 hours (\pm 12 hrs) for D-dimer, activated Protein C levels and plasmin-antiplasmin complexes measurements. Excluding r-TEG analysis and PT/ INR measurements, all blood and serum samples will be spun, stored and batched at their respective institution and delivered to the University of Pittsburgh where formal ELISA immunoassay measurements will be undertaken. Those laboratory/mechanistic outcomes including flow cytometry which require fresh blood samples will be performed only at the University of Pittsburgh on a subset of patient samples unless participating centers have specific capabilities and following appropriate training for standardization.

I.5.1. Coagulopathy and TEG parameters (Aim#2): To appropriately characterize differences in coagulopathy between tranexamic acid and placebo, in addition to r-TEG measurements of hyperfibrinolysis, presenting PT/ INR and additional TEG parameters will also be measured (ACT, r-value, k-time, α -angle, maximal amplitude, and G-values). All rapid TEG measurements will be performed within 6 hours of arrival and at 12 and 24 (+/- 12 hours) hours post injury. TEG analysis will be performed on a TEG[®] 5000 Thromboelastograph[®] Hemostasis Analyzer which will reside within the emergency department of each participating site. Standard laboratory INR will be drawn and measured at each institution within 6 hours of arrival and at 12 and 24 hours (+/- 12 hours). To further quantify the coagulopathy and hyperfibrinolysis post injury in these patients, D-dimer, activated Protein C levels and plasmin-antiplasmin complexes will be measured by ELISA plate assay. (ANIARA, USCN Life Science Inc., DRG International, Inc.) Plasmin-antiplasmin complexes may represent a more common, subclinical measurement of fibrinolytic activity that is not able to be assessed using standard TEG analysis, but elevated levels are associated with significantly worse outcome post injury and may be a marker than demonstrates the mechanism by which tranexamic acids has it beneficial effects.

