I.5.2. Exploratory Inflammatory Response Outcomes (Aim#3): Plasmin has pro-inflammatory effects by activating monocytes, neutrophils, platelets, endothelial and dendritic cells and induces pro-inflammatory genes.^{51,52} Plasmin also induces chemotaxis of monocytes and dendritic cells and in-vitro and in-vivo studies have demonstrated the ability of plasmin to stimulate the production reactive oxygen species and promote the release of lipid mediators and cytokines via complement activation.^{51,53} To appropriately characterize the potential non-antifibrinolytic mechanisms responsible for the mortality benefit attributable to tranexamic acid, serum plasmin levels, and plasmin mediated compliment activation (C3a and Factor B) and HMGB1 levels will be measured by ELISA plate assay for all enrolled patients (MyBioSource, BD Biosciences). A Cytokine 10-plex Panel for the Luminex[®] platform will be utilized for all early inflammatory cytokine measurements. (Novex[®]) These same inflammatory response measurements will be utilized for the randomized dose regimen comparison at 12 and 24 hours post injury.

I.5.3. Platelet, Leukocyte and Inflammatory Gene Expression Measurements (Aim#3): To further characterize an anti-inflammatory effect of tranexamic acid mediated thru reduced plasmin activation, for those patients enrolled at the University of Pittsburgh, whole fresh blood will be obtained and platelet and leukocyte activation will be measured on a subset of patient samples using flow cytometry (FACS) analysis utilizing platelet activation specific antibodies (CD41 and CD62P, Molecular Probes[®]) and Leukocyte activation specific antibodies (CD11a and CD35, Molecular Probes[®]). Inflammatory gene expression will be assessed via RT-PCR with a focus on evidence based gene targets including those identified as being most dramatically perturbed following severe injury from the *Glue Grant* study cohort including CD177, MMP8, lactotransferrin, haptoglobin, S100A8 (calgranulin), MYBL1

(myeloblastosis viral homologue, v-myb), KLRF1 (Killer cell lectin like receptor subfamily F, member 1), TGFBR3 (TGF- β receptor III subunit), and TCRA (T cell receptor α subunit).⁹⁴ These studies will be performed at a University of Pittsburgh FACS and RT-PCR core facilities which will be available 24 hours/day over the three years of the study.

J. Analysis Plan:

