
J.2. Analysis of Prehospital Randomized Secondary Outcomes: Unless there is sufficient power (predetermined before the analysis is begun), the approach to analysis of secondary endpoints will generally be calculation of confidence limits on intervention group differences or model parameters rather than formal tests of significance at a specified critical level as the trial will not have sufficient power to detect difference in all of these outcomes. However, these comparisons will add to the knowledge of the benefits and risks of the interventions. Parametric and nonparametric comparisons will be applied according to normalcy. All tests used will be two-tailed tests at significance level (α) of 0.05. For prehospital randomized clinical outcomes we will use Chi-square with 95% confidence intervals for dichotomous outcomes and parametric or non-parametric testing for continuous variable with 95% confidence intervals. For prehospital randomized laboratory or exploratory outcomes we will use parametric or non-parametric testing for continuous variable with 95% confidence intervals.

J.3. Analysis for Second Stage In-hospital Randomized Dosage Regimens: Chi-square test will be able to test the effect of different tranexamic dosage regimens on hyperfibrinolysis. Similarly, chi-square will be used to detect any differences between dosage groups for 30 day mortality. To detect a trend in dosage response, test for trend will be implemented. As additional analysis and to account for site and to adjust for some important covariates, we will use logistic regression to test the effect of dosage on hyperfibrinolysis. Similarly Cox proportional hazards regression can be used for 30 day mortality. *For In-hospital randomized dosage regimen comparison for clinical outcomes* we will use Chi-square with 95% confidence intervals for dichotomous outcomes and parametric or non-parametric testing for continuous variable with 95% confidence intervals. *For In-hospital randomized dosage regimen comparison for laboratory or exploratory outcomes* we will use parametric or non-parametric testing for continuous variable with 95% confidence intervals.

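### Serum markers are assayed in yearly batches but analysed without a batch term; if batches shift, some precision is lost, with no bias.

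*Combined protocol and SAP*

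**What the plan says.** Section F sets the shipping schedule: "Serum for cytokine and ELISA measurements will be batched and sent to the University of Pittsburgh on an annual basis". Section A has Year 1 samples batched for plate assay, and says of Year 2 that "blood samples will again be batch analyzed for plate assay analysis". Section I.5 excepts r-TEG and PT/INR. For the rest, "all blood and serum samples will be spun, stored and batched at their respective institution and delivered to the University of Pittsburgh", where the immunoassays are run. Sections I.5.1 and I.5.2 list D-dimer, activated protein C, plasmin-antiplasmin, plasmin, C3a, Factor B, HMGB1 and a ten-cytokine panel. On coverage, I.5.2 states that "HMGB1 levels will be measured by ELISA plate assay for all enrolled patients".

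For the prehospital comparison J.2 says: "For prehospital randomized laboratory or exploratory outcomes we will use parametric or non-parametric testing for continuous variable with 95% confidence intervals". It adds: "All tests used will be two-tailed tests at significance level (α) of 0.05". J.3 uses matching wording for the three in-hospital regimens. Neither section names a batch, run or plate term, and the documents mention no bridging samples or normalisation between batches. Site is accounted for in the 30-day mortality analysis (J.1.1) and in the dose-regimen model for hyperfibrinolysis (J.3), but not for these markers.

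On allocation, H.5.1 says patients are "randomized using an allocation sequence block size of 8 to either 1 gram of tranexamic acid or placebo". H.5.2 describes the second stage: "An allocation sequence based upon a block size of 9 again generated with a computer random number generator".

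**The concern.** Results from assays run a year apart can differ in level for reasons unrelated to the patients. If all values are pooled and compared without regard to batch, that difference is counted as patient-to-patient variation and the standard error grows. J.2 intends secondary outcomes to be reported mainly as confidence limits, so interval width is itself the reported result. What is at stake is the precision of 17 secondary and exploratory markers (seven named proteins and ten cytokines). They support the ELISA part of Aim 2, the serum part of Aim 3 and the laboratory part of Aim 4.

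**Working it through.** **The plan's own figure.** The only sample size stated is for 30-day mortality. A two-sided pooled z test of 16% against 9.65% with 497 per arm gives power 0.8505, which matches the stated 0.85. The plan gives no SD, power or assay variance for any marker, so this supplies only the number of patients.

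**Inputs.** From section A: 330 patients in Year 1 and 330 in Year 2. The remainder is 994 − 660 = 334, taken here as a third yearly batch. From H.5: blocks of 8 issued per helicopter base or ground station, and blocks of 9 for stage 2. Assumed, because the documents are silent: the share *f* of total marker variance due to batch (5% to 30%), and 20 bases.

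**Balance and bias.** In a simulation with those inputs (3,000 trials per setting), the largest departure from 50:50 in any yearly batch averaged about 1.3 percentage points. Batch is therefore almost unrelated to arm, and the estimated difference is almost unaffected. With no true effect, the unadjusted test rejected in 3.9%, 3.6%, 3.2% and 2.6% of trials for *f* = 5%, 10%, 20% and 30%. These rates are below the nominal 5%, so the error is on the conservative side.

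**Width.** With balance, an unadjusted interval uses the total variance and an adjusted one uses the within-batch variance.

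- If *f* is the share actually realised in the trial, the width ratio is 1/√(1 − *f*).
- If *f* is a variance component and only three batches are drawn, the expected realised between-batch variance is (2/3)*f*. The ratio is then roughly √(1 + (2/3)*f*/(1 − *f*)). This slightly overstates the average ratio.

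For a comparison with 80% power when adjusted (2.80 standard errors), the unadjusted power under the first definition is Φ(2.80 − 1.96/√(1 − *f*)).

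| *f* (assumed) | Excess width, realised share | Excess width, variance component | Unadjusted power, realised share |
|---|---|---|---|
| 5% | 2.6% | 1.7% | 79% |
| 10% | 5.4% | 3.6% | 77% |
| 20% | 11.8% | 8.0% | 73% |
| 30% | 19.5% | 13.4% | 68% |

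For the realised share, simulation gave width ratios of 1.026, 1.054, 1.118 and 1.196. Unadjusted coverage was 96.1%, 96.4%, 96.8% and 97.4%, while adjusted coverage stayed near 95%. For the variance component, simulation gave mean excesses of about 2%, 4%, 8% and 12%. At *f* = 0 the two intervals had the same width (ratio 0.9998).

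**Dose regimens.** The ratio does not involve group size, so the same percentages apply in J.3, where each regimen has about 497/3 = 166 patients. A simulation of three regimens in blocks of 9 gave the same realised-share ratios to two decimals.

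**Plates.** Three samples from 330 patients are about 990 per marker per year, so each yearly batch spans many plates. Blocks issued per base do not balance arms within a plate. Assuming 13 to 25 patients per plate placed at random, unadjusted coverage stays at about 95%. With no plate shift, plate as a fixed factor widens intervals by 2% to 4% and costs 2 to 3 points of power.

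**The case against.** The case for leaving the plan alone has several parts.

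- **Nothing is invalid.** This stands. A reader might infer that yearly batching biases the comparison of arms or produces false positives. The near-balance within years rules that out.
- **A batch term is not forbidden.** J.2 allows confidence limits on model parameters, and its wording on laboratory tests is general. This also stands: the plan leaves the term unspecified rather than excluding it. But leaving the choice open for 17 markers until the data are seen is avoidable, and if the batch is not recorded at assay, adjustment may be impossible later.
- **The size is assumed.** This stands. One laboratory runs the immunoassays with named suppliers. That does not exclude shifts, but nothing in the documents supports the upper end of the range. A reader might infer that the intervals will be wider than they need be. The documents support that only if a shift exists.
- **The markers are subordinate.** Largely right. Aim 2 leads with hyperfibrinolysis and traumatic coagulopathy, measured by r-TEG and INR on site and not batched. Aim 3 also includes flow cytometry on fresh blood. J.2 already concedes that power is not sufficient for all secondary outcomes.
- **Finer stratification is not free.** A reader might go on to stratify by plate. The plate figures above show why that does not follow.

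**Conclusion.** The point holds as a minor matter of efficiency. The batch-assayed markers are to be compared without a term for a known feature of how they are measured. If batches shift, the intervals are too wide by about 2% to 3% at an assumed 5% share, rising to about 12% to 20% at an assumed 30%. In each pair the lower figure treats the share as a variance component over three batches and the higher figure treats it as the realised share. If there is no shift, nothing is lost. The conclusion rests on assays being run by year, as sections A and F indicate, on near-balance within years, and on a non-zero shift that the documents neither state nor quantify. It does not touch 30-day mortality, INR, r-TEG or flow cytometry.

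**What to change.** Record the assay batch and plate with every ELISA and Luminex result. In J.2 and J.3, specify for each batch-assayed marker a linear model on the log scale with arm (or regimen) and yearly assay batch as fixed factors, and report the within-batch difference with its 95% CI. For the two-arm comparison in J.2 only, a van Elteren test may serve as the rank-based alternative. It is a two-group test and gives no interval by itself, so it does not suit the three regimens of J.3. Do not enter plate as a fixed factor by default.

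The cost is one recorded variable (assay batch and plate), a sentence in each of J.2 and J.3, and about two degrees of freedom (three batches less one) out of nearly 1,000. No further samples or assays are needed.

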hospital and prehospital clinical trials. All enrolling centers and respective investigators similarly have busy emergency medical services and significant experience with multi-center trials, the research infrastructure to allow them to successfully occur and have no other clinical investigations that would preclude participation in the current proposal. *Participating Institutions include: University of Pittsburgh, University of Arizona, University of Texas at San Antonio, and the University of Utah. The University of Tennessee at Memphis will be utilized as an alternate/additional site if required.*

H.2. Study Population: The study population will include blunt or penetrating injured patients at risk of hemorrhage being transported via emergency medical services from the scene of injury or from referring hospital to a definitive trauma center that is participating in the trial. We have selected similar inclusion criteria as the prior large, prospective study⁴¹ (CRASH-2). This represents a similar level of acuity than the CRASH-2 study and additionally allows the mechanism of tranexamic acid's benefit to be characterized across a spectrum of injury severity since the pre-specified analysis of the CRASH-2 trial demonstrated that the mortality benefit attributable to early tranexamic acid remained consistent across patients with low thru high predicted mortality, suggesting its use should not be limited to the most severely injured.⁴⁴ The study group may also contain traumatic brain injured patients who represent a subgroup that may also benefit from early tranexamic intervention.⁴⁵ Based upon our own current data (2011-2012) in injured patients that require air medical transport, these inclusion criteria are associated with over a 65% blood transfusion rate in the first 24 hours from admission and represents the most pertinent population for the trial.

H.2.1. Specific Inclusion Criteria:

1. Blunt or penetrating injured patients at risk of hemorrhage being transported via emergency medical services from the scene of injury or from referring hospital to a definitive trauma center that is participating in the trial

AND

2. Within 2 hours of estimated time of injury

AND

3A. Hypotension (Systolic Blood Pressure (SBP) < 90mmHg)

i. At scene of injury or during emergency medical transport

ii. Documented at referring hospital prior to emergency medical transport arrival

OR

3B. Tachycardia (heart rate >110 beats per minute)

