J.7. Missing Data: For 30-day mortality, given the transient nature of many of the subjects, extensive efforts will be made to ascertain vital status (see N.6.). Batch searches of the mortality databases will continue every quarter for subjects with unknown status, until trial closeout. For interim and final analyses, subjects who have not been reported as deceased by day 30 following ED admission from any of these sources we will use multiple imputation for the final value. As sensitivity analyses we will report the data with and without imputation. We will also report an analysis consistent with that used in other studies counting those missing as alive on day 30.

K. Sample Size Justification and Power Analysis:

We have determined the sample size for this proposal and powered the analysis based upon the primary outcome, 30 day mortality.

K.1. Primary Outcome 30 day mortality: Assuming a baseline mortality risk of 16% as was demonstrated in the Crash-2 study^{41,43} with 30 day mortality as the primary outcome, using a two-sided Z test with pooled variance and a 2 sided alpha of 0.05 the study will have a 90% power to detect a 7% or greater difference in 30

day mortality. The study will have 80% power to detect a 6% or greater difference in 30 day mortality. Using this power analysis, **497 patients in each arm, 994 total patients will be required, with a power of 0.85 and 2 sided alpha of 0.05. This will require on average each center to enroll 80 patients per year or 1 to 2 per week.** As busy, level 1 trauma centers with robust emergency medical programs were screened using the proposed inclusion criteria over 2012 data and selected for participation based upon this information, this sample size estimate is appropriate and attainable.

Power	Sample Size Grp 1 N1	Sample Size Grp 2 N2	Prop H1 Grp 1 or Trtmnt P1	Prop Grp 2 or Control P2	Diff if H0 D0	Diff if H1 D1	Target Alpha	Actual Alpha	Beta
0.9000	497	497	0.0919	0.1600	0.0000	-0.0681	0.0500		0.1000
0.8500	497	497	0.0965	0.1600	0.0000	-0.0635	0.0500		0.1500
0.8000	497	497	0.1003	0.1600	0.0000	-0.0597	0.0500		0.2000

L. Human Subjects:

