- Trial name: Study of Tranexamic acid during Air and ground Medical Prehospital transport (STAAMP) trial
- Principal investigator (PI): [name], MPH
- Funding agency: Department of Defense
- Trial design: Multi-center, prospective, randomized, blinded, controlled interventional trial.
- Phase: III
- Number of patients: 994
- Number of sites: 4

DSMB Description

- This DSMB will be coordinated by the PI, [name], MPH.
- This DSMB will be independent of the investigators, funding agency, regulatory agencies, and institutional review boards.
- This charter will be approved by its DSMB members as attested to by signature of the chairperson.

DSMB Membership

- Members will disclose conflicts of interest and will be cleared of significant conflicts of interest and potential conflicts of interest in accordance with provisions in this charter.
- DSMB members will sign confidentiality agreements covering DSMB activities.
- Composition of membership will be researchers with the following expertise: hematology (transfusion medicine), surgery (trauma/critical care), prehospital emergency medicine, epidemiology (clinical trial design), and biostatistician.
- Remuneration will be provided any expenses related to DSMB activities.

Reporting

- Unblinded data to be reviewed by the DSMB will be provided by an independent statistician. Issues and recommendations identified by the DSMB will be provided to the principal investigator by the DSMB chairperson in accordance with this charter.
- Details of closed session deliberations (e.g., minutes) will be considered privileged and not subject to disclosure except as required by law.

Introduction

The purpose of this charter is to define the roles and responsibilities of the DSMB, delineate qualifications of the membership, describe the purpose and timing of meetings, provide the procedures for ensuring confidentiality and proper communication, and outline the content of the reports.

The DSMB will function in accordance with the principles of the following documents: FDA document "Guidance for Clinical Trial Sponsors: On the Establishment and Operation of Clinical Trial Data Monitoring Committees".

Study Overview/Summary

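### K.1's required rate of 80 patients per centre per year, and F's expected 70, both fall short of 994 patients from the four named sites in 33 months; about 90 is needed

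*Combined protocol and SAP*

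**What the plan says.** **Expected rate and duration (F, Project Milestones).** "We expect approximately 70 patients per year per institution on average". The same section sets enrolment at 33 months, which it equates to 2.75 years. Start-up takes 1.5 months before that and wind-down 1.5 months after it.

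**Required rate (K.1).** After fixing 497 patients per arm, 994 in total, K.1 states: "This will require on average each center to enroll 80 patients per year or 1 to 2 per week". It concludes that the sample size can be attained.

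**Sites.** H.1 names four institutions: "University of Pittsburgh, University of Arizona, University of Texas at San Antonio, and the University of Utah". It adds a reserve: "The University of Tennessee at Memphis will be utilized as an alternate/additional site if required". The DSMB charter (Appendix 3) lists "Number of sites: 4" next to 994 patients. The blank reporting tables in Appendix 4 have columns for five centres.

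**Trial-wide projection (Statement of Work).** For Year 1, after a one-month training period, "trial enrollment will begin with an estimated 330 patients enrolled by years end". Year 2 adds another 330, for a total of 660.

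**The concern.** K.1 and F give different per-centre rates for the same trial, and the one labelled as expected is 12.5% below the one labelled as required (70 against 80). Neither reaches 994 when multiplied by the four named sites and the stated window.

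The 994 underlies the power table in K.1 and the look sizes of 166, 332 and 497 per arm in P.4. The calendar has no slack: 1.5 + 33 + 1.5 = 36 months, which is the whole three-year trial. A reader judging feasibility cannot tell from the protocol whether the reserve site is needed, whether enrolment must run past 33 months, or what happens if neither occurs.

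**Working it through.** **1. The plan's own size and power.** Inputs from K.1: control mortality 0.16, two-sided alpha 0.05, pooled-variance z test, 497 per arm. Recomputed power is 0.900 for 0.0919 versus 0.16, 0.850 for 0.0965, and 0.800 for 0.1003. These match the K.1 table. The three-look O'Brien-Fleming design in P.4 also reproduces: total alpha 0.050, and power 0.800 at the stated drift of 2.82089.

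**2. Accrual.** Patients = sites × rate × years, with every site open for the whole window at a constant rate. Months to target = 994/(sites × rate) × 12.

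| Sites | Rate per centre per year | Patients in 2.75 years | Against 994 | Months to 994 |
|---|---|---|---|---|
| 4 | 70 | 4 × 70 × 2.75 = 770 | −224 (22.5%) | 42.6 |
| 4 | 80 | 4 × 80 × 2.75 = 880 | −114 (11.5%) | 37.3 |
| 5 | 70 | 5 × 70 × 2.75 = 962.5 | −31.5 (3.2%) | 34.1 |
| 5 | 80 | 5 × 80 × 2.75 = 1,100 | +106 | 29.8 |

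**3. Rate needed for 994.**
- Four sites, 33 months: 994/(4 × 2.75) = 90.4 per centre per year.
- Five sites, 33 months: 994/(5 × 2.75) = 72.3.
- Four sites, 36 months: 994/(4 × 3) = 82.8.

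K.1's 80 lies closest to four sites enrolling for the full three years, and F's 70 closest to five sites for 33 months. The protocol does not say how either was obtained.

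**4. Statement of Work.** Spread over four sites, 330 per year is 330/4 = 82.5 per centre. In Year 1 one month goes to training, so 330 in the remaining 11 months is 30 per month, or 30 × 12/4 = 90 per centre per year. On either reading it differs from both 70 and 80.

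**5. Power if enrolment were to stop short.** For n per arm and 0.10 versus 0.16 (mean 0.13):

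power = Φ[(0.06 − 1.96 × √(2 × 0.13 × 0.87/n)) / √((0.10 × 0.90 + 0.16 × 0.84)/n)]

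- n = 497: (0.06 − 1.96 × 0.02133)/0.02125 = 0.856, power 80.4%.
- n = 440 (880 patients): (0.06 − 1.96 × 0.02267)/0.02258 = 0.689, power 75.5%.
- n = 385 (770 patients): (0.06 − 1.96 × 0.02424)/0.02414 = 0.517, power 69.8%.

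With the three-look boundaries the values are 80.0%, 75.1% and 69.4%. For K.1's 85% scenario (0.0965 versus 0.16) the fixed-sample values are 85.0%, 80.5% and 75.1%. Five sites at 70 (962.5 patients) would give 79.1% for 0.10 versus 0.16 and 83.9% for 0.0965 versus 0.16.

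**The case against.** **The power is not wrong.** A reader might infer that the trial lacks its stated power. The documents do not support that. Power is stated for 497 per arm and is correct for that number. The boundary table sets its looks at fractions of accrual. F places wind-down after enrolment is complete, and no section says that the trial would close at 33 months with whatever number it had. Slow accrual would first mean a longer trial or an added site. This objection stands in full, so any loss of power is conditional.

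**A fifth site is available.** H.1 holds one in reserve and Appendix 4 has columns for it. At 80 per year, five sites more than suffice. At 70 they reach about 97% of target in 33 months, at a cost of about one point of power. This stands, but only if the site is open from the start. H.1 makes it conditional and the charter counts four.

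**K.1 also says 1 to 2 per week.** That is 52 to 104 per year, which contains 90.4. It also contains 70 and 80, so it does not settle which rate is required.

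**Other reassurance.** D.7 reports more than 150 patients meeting criteria in 12 months on the air services to be used, F monitors enrolment by centre every six months, and the charter allows the sample size to be re-evaluated. These are relevant, but eligible transports are not enrolments, and F still expects 70.

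**The Statement of Work.** A reader might multiply 330 by 2.75 and claim a third shortfall. That removes start-up time twice, because Year 1's 330 already follows the training month. The third-year entry is also not in the text available here, so no three-year total is drawn from it.

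**Conclusion.** The accrual statements contradict one another, and the rate that K.1 calls required is too low for the plan as written. For four sites over 33 months it should be about 90 per centre per year, not 80. At F's expected 70, four sites give 770 patients and need about 43 months to reach 994. If the reserve site is open from the start, the need falls to about 72 per centre per year, and 70 reaches 994 in about 34 months.

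This is a feasibility inconsistency, not an error in sample size, test or boundaries. The drop in power for 16% versus 10%, from 80.4% to 75.5% or 69.8%, applies only if enrolment closed at 33 months with four sites. The accrual figures assume all sites active throughout at a constant rate; a late-opening fifth site would contribute less. No dropout allowance was added, because K.1 has none.

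**What to change.** 1. In K.1, correct the required rate to about 90 patients per centre per year for four sites over 33 months, or about 72 for five sites over the same period.
2. Put F, H.1, K.1, the Statement of Work and the DSMB charter on one stated basis of number of sites, rate and duration.
3. If 70 per centre per year remains the expectation, state one of two things: that the fifth site is needed (994 in about 34 months if open from the start), or that four-site enrolment takes about 43 months.
4. State that enrolment continues until 994. If it may stop at 33 months, give the power at the number then expected.

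The cost is wording in those sections. The sample size, analysis and stopping boundaries need no change. The feasibility statement in K.1 becomes less favourable, and a longer enrolment period would extend the three-year calendar.
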